2.1 Aim

This study aimed to evaluate the effectiveness of virtual reality (VR) distraction in alleviating preoperative anxiety among patients scheduled for abdominal surgery

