2.5 Sample Size

The sample size was calculated based on the study by Mosso et al. (2009) using G*Power 3.1.9.7 software. With an effect size of $d=0.920$, $\alpha=0.05$, and $\text{power}=0.95$, a total of 96 patients were required (32 in each group).

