3.2 Procedures

Evaluation 1 (T1):

- Conducted in the patient's room in the morning.
- Informed consent obtained; forms and baseline anxiety/stress measurements completed.

Evaluation 2 (T2):

- Conducted 10–15 minutes after intervention or rest period

Virtual Reality Group:

- Watched a 2-hour 4K virtual forest video (<https://www.youtube.com/watch?v=uEMmpJgaXvo>).
- Used Zore G04E VR Shinecon headset with headphones and disposable eye covers.
- The researcher observed for any adverse effects.

Placebo-Video Group:

Watched the same video on a smartphone using disposable headphones

Control Group

No intervention; second evaluation conducted after ~15 minutes of rest.

4. Ethical Considerations

Approval was obtained from the Trakya University Ethics Committee (TÜTF-GOBAEK 2022/240) and the hospital administration (E-51088030-100-317619). All participants provided verbal and written informed consent. The study adhered to the Helsinki Declaration and CONSORT guidelines

5. Statistical Analysis Plan

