5.2. Descriptive Statistics

- Continuous variables (e.g., age, anxiety, stress): Mean, SD, median, min, max
- Categorical variables (e.g., gender, education, chronic diseases): Frequency and percentage

5.3.Normality Testing

Shapiro-Wilk test for all continuous variables

5.4.Inferential Statistics:

-Between-Group Comparisons:

Kruskal-Wallis H Test for comparing continuous variables across the three groups

Mann-Whitney U Test with Bonferroni correction for post-hoc pairwise comparisons

-Within-Group Comparisons (T1 vs. T2):

Wilcoxon Signed Ranks Test

-Categorical Variables:

Pearson Chi-Square Test

5.5.Statistical Significance

Significance level set at $p < 0.05$

Confidence interval: 95%

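### Section 5.4 names T1 only in within-arm tests and does not say that efficacy rests on the between-arm tests; a T1-adjusted comparison of T2 should be added

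*Combined protocol and SAP*

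**What the plan says.** The aim in section 2.1 is to "evaluate the effectiveness of virtual reality (VR) distraction in alleviating preoperative anxiety", which calls for a contrast between VR and another arm. Section 3.2 has anxiety and stress measured at T1 in every patient and again at T2.

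Section 5.4 lists two kinds of test on these scores:

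- Between arms: "Kruskal-Wallis H Test for comparing continuous variables across the three groups", followed by "Mann-Whitney U Test with Bonferroni correction for post-hoc pairwise comparisons".
- Within arms: "Within-Group Comparisons (T1 vs. T2", by "Wilcoxon Signed Ranks Test".

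T1 appears by name in section 5 only in the within-arm line. The between-arm lines do not say whether they are applied to T1, T2 or change, name no outcome and mention no adjustment for baseline. No sentence ranks one kind of test above the other, and section 5.5 sets a single 0.05 level for all of them. Section 2.5 states that "a total of 96 patients were required (32 in each group"), from d = 0.920, alpha 0.05 and power 0.95.

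**The concern.** The only stated analysis of change from T1 is carried out one arm at a time, and such a test cannot compare VR with anything. Reporting it is not an error in itself. The difficulty is that nothing stops a reader, or the trial report, from taking a significant fall in the VR arm beside a non-significant one in control as proof that VR works. That pattern can arise when VR does nothing, and it can be missing when VR works, because the control arm's fall is significant too.

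The second cost is efficiency. If the between-arm tests are run on T2 alone, a baseline score held for every patient is left out of the comparison that matters. That loses power whenever T1 and T2 are correlated.

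**Working it through.** **1. The plan's own figure.** Inputs from section 2.5: d = 0.920, alpha 0.05 (taken as two-sided), power 0.95. A two-sample t-test needs 31.70, so 32 per arm (power 0.952 at 32 and 0.946 at 31), and 3 × 32 = 96. A paired t-test would need 17.40. The stated size is therefore reproduced as a between-arm calculation.

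**2. The misleading within-arm pattern.** The documents give no SD, change or T1–T2 correlation (r), so these are assumed. Let p be the chance that one arm's Wilcoxon test is significant. With no VR effect and the same true change in both arms, P(VR significant, control not) = p(1 − p).

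- No change: p = 0.05, so 0.05 × 0.95 = 0.0475.
- The largest possible value is 0.5 × 0.5 = 0.25.

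Simulation (20,000 trials per setting, 32 per arm, normal data with SD 1, r = 0.6, no VR effect):

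| Shared fall (SD) | 0 | 0.2 | 0.32 | 0.5 | 0.8 |
|---|---|---|---|---|---|
| VR significant, control not | 4.3% | 17.7% | 24.8% | 12.9% | 0.2% |
| VR significant, both others not | 4.0% | 13.7% | 12.8% | 1.9% | 0.0% |

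A separate run at r = 0.5 and 0.7 gave 16–25% for shared falls of 0.2 to 0.4 SD.

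The 25% limit needs equal true change. If change differs by arm, the rate is p_VR(1 − p_control), which has no such limit. With an assumed time-related fall of 0.3 SD in the VR arm alone and no VR effect, two simulations gave 41–43% at r = 0.6 and 66–67% at r = 0.8.

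The pattern also misses real effects. With a VR-only benefit of 0.5 SD, a shared fall of 0.32 SD and r = 0.8, it appears in 23% of trials, while the VR–control test of T2 adjusted for T1 detects the effect in 74%.

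**3. What T1 is worth between arms.** Relative to T2 alone (residual variance 1), adjusting for T1 gives 1 − r², and a change score gives 2(1 − r), which exceeds 1 when r is below 0.5. At r = 0.5 the adjusted variance is 1 − 0.25 = 0.75. In normal theory, power at d = 0.92 and level 0.05/3 = 0.0167 then rises from 0.885 to 0.961.

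Simulated VR–control power at 0.05/3, in the same set-up (rank ANCOVA: rank T1 and T2, regress, test the residuals):

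| Effect | r | T2 alone | Change | T2 adjusted for T1 |
|---|---|---|---|---|
| 0.5 SD | 0.4 | 31% | 26% | 37% |
| 0.5 SD | 0.6 | 31% | 39% | 47% |
| 0.5 SD | 0.8 | 31% | 73% | 74% |
| 0.92 SD | 0.4 | 86% | 78% | 91% |
| 0.92 SD | 0.6 | 86% | 94% | 97% |

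On a capped 0–10 integer scale (assumed mean 5, SD 2.5; effect 0.5 SD), T2 alone against adjusted T2 gave 30.3% and 35.9% at r = 0.4, 30.5% and 45.7% at r = 0.6, and 30.7% and 71.1% at r = 0.8.

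With no effect and equal change, overall three-arm error was 4.5–5.0% for Kruskal-Wallis on T2 and 4.7–5.2% for the rank ANCOVA.

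**The case against.** The strongest reply is that the plan already leans the right way. The between-arm tests come first, only they carry a multiplicity correction, and the sample size is a two-sample one. Under randomisation they are valid on T2 without any adjustment, and the phrase about continuous variables could cover change scores. Within-arm tests are routine. The gain at the plan's own d = 0.92 and r = 0.4 is modest (86% to 91%), and the larger gains rest on a correlation and an effect size that the documents do not give. Finally, sections 2.3 and 5.1 describe completed work, so an unlisted test chosen now should not become the sole basis for efficacy.

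Most of this stands. The listed between-arm tests should keep their place, and the adjusted analysis belongs beside them. What it does not answer is that the priority is implied and never stated, and that the variable under test is left open.

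A reader might also take the unequal timing in section 3.2 as an argument for adjusting for T1: the VR arm "Watched a 2-hour 4K virtual forest video", while for control the entry is "No intervention; second evaluation conducted after ~15 minutes of rest". It is not. Drift that differs by arm biases the between-arm test too. In the 0.3 SD drift example, the VR–control test at a nominal 1.7% rejected in about 11% of trials on T2 alone and 16% after adjustment at r = 0.6, and in about 9% and 27–28% at r = 0.8. Timing is a separate issue, and adjustment does not cure it.

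**Conclusion.** The point holds as one of unused baseline information and unstated priority. Section 5.4 has valid between-arm tests but does not say that they decide efficacy, what they are applied to, or that T1 enters them.

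Under equal true change, r = 0.6 and no VR effect, 'VR significant, control not' appears in about 5% of trials with no shared fall and about 25% with a shared fall of 0.32 SD. Adjusting T2 for T1 lifts VR–control power at 0.05/3 from about 31% to 37%, 47% and 74% at r = 0.4, 0.6 and 0.8 for a 0.5 SD effect, and from about 86% to 91% and 97% at r = 0.4 and 0.6 for d = 0.92. The correlation, the shared fall and the 0.5 SD effect are assumptions.

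Two stronger readings are tempting and not supported. One is that the plan bases efficacy on within-arm tests or lacks a proper comparison; it lists between-arm tests and was sized for one. The other is that 25% is this trial's false-positive rate, or a limit for any trial. It is the maximum under equal true change only, most assumed falls give less, and the rate can be higher if drift differs by arm.

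**What to change.** In section 5.4:

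1. State that efficacy conclusions rest only on between-arm comparisons, and that T1-to-T2 change within each arm is descriptive, reported with a 95% CI.
2. Apply the listed Kruskal-Wallis and Bonferroni-corrected Mann-Whitney tests to T2. Name the outcome (VAS-A for the anxiety aim) and the pairs of arms that the correction covers. If these tests have already been run on something else, report that as well.
3. Add a between-arm comparison of T2 adjusted for T1: a rank-based ANCOVA across the three arms with Bonferroni-corrected pairwise contrasts. This keeps the plan's non-parametric approach. Label it post hoc and report it beside the listed tests, not in place of them.

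A change score is not a safe substitute. Below a correlation of about 0.5 it is weaker than T2 alone (78% against 86% at d = 0.92 and r = 0.4), and the correlation is not documented.

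The cost is a few sentences and a small re-analysis of data already collected, with no new patients or measurements. The downside is that the adjusted result may differ from the listed tests, in which case both must be shown.
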